4. Quality of life (all visits): QoL will be measured using the PedsQL™ which is a modular approach to measure generic health related quality of life in both healthy children and adolescents, as well as those with acute and chronic health conditions. It consists of structured interview with the parents and the child with 23 items divided among 4 sub-scales to assess function in 4 domains: Physical; Emotional; social; and School. The instrument is brief, takes 15

minutes to administer, and is developmentally adjusted for a broad age range.

5. PTS : Modified Villalta's scale and Marilyn-Manco Johnson Instruments, the two validated PTS scales, will be used to diagnose and grade severity of PTS at the 6 month mark corresponding to Visit 2 and the 9 month mark (corresponding to Visit 3). The principal and co-investigators will complete PTS evaluations as is standard of care at Visit 2 and Visit 3. In addition, a blinded PTS assessment will also be completed by the physical therapist (currently routinely assigned to the Thrombosis and Bleeding Disorders Program) at both visits.
6. Medication adherence: Anti-Xa and INR will be collected for participants on lovenox and warfarin, respectively. Families with participants on Rivaroxaban will be asked to complete a medication log because no assay will be used to measure adherence for Rivaroxaban. The medication log will measure compliance with anticoagulation during active treatment period and will include the subject's specific anticoagulant, dose, and date and time medication was taken.

See appendix for copies of above questionnaires, administration and scoring procedures.

IV. PARTICIPANT TIMELINE

All study visits will coincide with standard-of-care visits for patients with VTE at our center. All visits will be allowed a time window to accommodate preferences of subjects and families \pm 2 weeks for visit 1 and \pm 4 weeks for visit 2 and 3.

Study assessments: (Table 1 for schedule of events).

V. MODIFICATIONS

a. RISKS

- i. Blood Draws: Risks associated with drawing blood include minimal discomfort and/or bruising, infection,

- excess bleeding, clotting, and/or fainting are possible.
- ii. Doppler Ultrasound: There are no risks from the sound waves used for ultrasound. The test is not painful and does not have any radiation. This will be done as per standard of care.
- iii. Skin irritation or allergies with wearing the activity tracker
- iv. Injuries or falls related to increased physical activity

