- v. As we plan to use an online data format to gather subject information, security of information may be a concern. Fitabase code and databases reside on the Microsoft Windows Azure Platform and rely on the robust security, both physical on-premise guarding, and over network, provided as part of that platform. Windows Azure runs in data centers that comply with key industry standards for security and reliability.
- vi. Loss of confidentiality related to use of protected health information (PHI).

b. BENEFITS

Study subjects may discontinue their participation at any time. However, information regarding the potential benefits to continue on the study will be made explicitly clear prior to their discontinuation.

- i. Whether or not the subject or their family consents, the schedule of the clinic visits will remain the same as proposed in the study. All patients with thrombosis are followed until they become adults with more frequent visits in the first 24 months after the acute event and then yearly afterwards.
- ii. Subjects will also derive benefit from the careful monitoring of activity after thrombosis as well as interval telephone calls to promote compliance and answer questions.
- iii. Successful monitoring after the acute thrombotic event is expected to improve their overall well-being and possibly prevent any physical, cardiac, cognitive and behavioral abnormalities resulting from thrombosis.

- iv. Subjects will be provided with custom fitted compression stockings as part of the study. Compression stockings help to relieve swelling and pain and reduce the risk of developing post-thrombotic syndrome after a DVT. Although prescribed for all post DVT patients, many do not use them due to the expense of the stockings and lack of availability.
- c. Every effort will be made to retain study subjects in the trial for the entire ~9 months to enable complete follow-up and data collection.

V. WITHDRAWAL/TERMINATION

- a. Subjects that 'No Show' for Visit 2, are unable to provide >80% of the 'steps/day' data and are unable to be contacted/rescheduled. Data already collected will be used in the analysis.
- b. Subjects for whom an alternative diagnosis discovered.
- c. In the investigator's medical opinion, it is best to withdraw the subject from the protocol

VI. CONCOMITANT CARE

- a. Patients who initially receive thrombosis care elsewhere prior to enrollment may participate in the study if all eligibility criteria are met.

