- b. Subjects who need to continue long term prophylactic anticoagulation will still be eligible and will be included at discretion of their attending hematologist.
- c. The activity tracker, the Fitbit, is made up of a flexible durable material used in many sports watches (and one that does not contain latex) with a surgical grade stainless steel clasp and contains traces of nickel. It is meant to be worn day and night on the wrist. Because there's a possibility of skin irritation and allergies with any type of jewelry, all participants in this study will be warned and care and wearing tips will be provided. They will be monitored for any skin problems during the clinic visits and a treatment plan will be made in collaboration with their primary pediatrician should any skin irritation develop. I will ask to be notified immediately of any such occurrence at home and will then contact the participant or the family to assess

their clinical condition and make a treatment plan based on the severity of the skin condition.

VII. OUTCOMES AND POWER CALCULATIONS

Primary Outcomes will be 1) **feasibility indicators (Table 2)** measured throughout trial. The level of adherence in the intervention group will be calculated as the proportion meeting the weekly steps/day goal during the 'active' 8-week period of the total 16 weeks of intervention as determined by the Fitabase data platform output, and 2) **change in clinical outcomes**

such as PTS biomarkers at baseline and Visit 2, and QoL (at all visits). Secondary outcome: I will assess for PTS with validated scales at the 6 and 9 month follow-up visit as is standard of care.

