Analyses: The objectives of this trial are to assess the feasibility of the design and to measure the effect size of the intervention. All analyses will therefore be descriptive and will be performed once, at the end of the trial. Means and standard deviations, or when appropriate, medians and semi-inter-quartile ranges will be used to describe demographic and clinical characteristics. Reasons for non-eligibility, lack of consent, dropout and lack of compliance will be documented. For feasibility indicators, we (study investigators and [name]-biostatistician) will describe rate of eligibility (proportion of subjects screened who fully meet trial eligibility criteria to participate in the trial), rate of consent (the proportion of eligible subjects who consent to participate) and rate of loss to follow-up (proportion of randomized subjects who drop out of the trial, in total, and by allocated intervention). We will also describe the level of compliance in the intervention group, calculated as the ratio of who complied with the activity prescription to the number given the prescription. We will consider the trial *successful* if the following criteria are met: rate of eligibility $\geq 30\%$, rate of consent $\geq 30\%$, rate of loss of follow-up $<20\%$, level of compliance $\geq 60\%$ and proportion of subjects who complete the trial $\geq 80\%$. For the clinical outcomes (including the secondary outcomes), we will describe change (means and standard deviations) in the intervention and control groups, from baseline to 6 month, in the QoL scores and PTS biomarkers. Each change score will be interpreted for clinical significance and common responses counted for frequency of occurrence. The impact of the activity

Table 2: Feasibility Indicators

Proportion of screened subjects who meet eligibility criteria: $\geq 30\%$

Proportion of screened subjects who provide consent: $\geq 30\%$

Level of adherence in the intervention arm: $\geq 60\%$

Proportion of subjects who complete the trial: $\geq 80\%$

tracker to promote continued physical activity in the last 2 weeks of the 12-week period would be explored. We will also assess the impact of covariates such as age, sex, BMI, baseline activity, intensity of activity over and above the activity prescription, on change scores.

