Sample size calculation: For reasons of practicality and cost, we have decided to limit the size of this pilot RCT to 44 subjects (20 in each arm; 22 after considering a 20% drop out rate). We anticipate that the probable primary outcome for the larger trial will be change in rate of PTS development and/or progression. This trial may also provide compelling preliminary data for future studies. For example, if this intervention reduces the risk of PTS from 26% (known probability of PTS) to 10%, this pilot study has 71% chance of showing a promising trend (p-value<0.2) that the intervention reduces the risk of PTS. We acknowledge that the small size of this pilot study limits the validity of the findings; therefore, we will be cautious with such analyses.

I. RECRUITMENT

- a. Information about the clinical study will be provided via direct communication by study investigators and physicians at Children's Medical Center including ED physicians, hospitalists, and general pediatricians attending on the inpatient medicine services and outpatient continuity clinic as well as house officers.
- b. Information regarding the study will be available on the University of Texas Southwestern clinical trials website and at clinicaltrials.gov.
- c. Potential subjects will be identified through review of new patient referrals to Children's Medical Center, inpatient admissions and/or consultations for thrombosis.
- d. Each subject will receive financial compensation for participation. Payment will be made at completion of the study visits at Visits 1 and 2 (\$25 each) and at the end of Visit 3 (\$50) based on attendance and return of the tracking logs.
- e. Expected recruitment rate will be 2-3 participants per month.
- f. Duration of recruitment period is expected to be approximately 24 months.

- g. Assessment of study recruitment and retention will be performed when 20 participants have been enrolled on the study, or at approximately 9 -12 months.

II. DATA COLLECTION, MANAGEMENT AND ANALYSIS

a. DATA COLLECTION METHODS

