using mean (standard deviations [SD]) for continuous outcomes, and raw counts (%) for categorical outcomes are reported. For the clinical end points, using an intent-to-treat analysis that includes all participants with data at baseline and 6 months (end of the intervention period), within-patient change from baseline (diagnosis or pre-VTE levels) to 6 months (mean, SD) in the physical activity will be compared to standard care in the following measures: D-dimer, FVIII, CRP, thrombin generation assay parameters of endogenous thrombin potential and peak thrombin, fibrinolysis on thromboelastography, QoL (total and physical), selfreported physical activity levels, and PTS (change from 6 to 9 months). This will be averaged for each group, and within-group differences will be compared between the standard care and physical activity groups using a t test. ECS use will be descriptively described but not included in a formal analysis.

ETHICS AND DISSEMINATION

I. RESEARCH ETHICS APPROVAL

This protocol and template informed consent forms will be reviewed and approved UT Southwestern IRB with respect to scientific content and compliance with applicable research and human subjects regulations. Subsequent to initial review and approval, the investigators will submit progress reports to the IRB at least annually and at study closure.

II. PROTOCOL AMMENDMENTS

Any modifications to the protocol, which impact the conduct of the study, or potential risk/benefit of the participants, will require a formal amendment to the protocol with IRB approval.

III. CONSENT OR ASSENT

Informed consent will be obtained after information has been provided to patients' families along with a discussion of the risks and benefits along with opportunity for questions. Consent forms will be provided for all parents involved in the trial.

IV. CONFIDENTIALITY

Records of each patient's participation in this study, including the original informed consent document, will be kept in a locked file cabinet in the Center for Cancer and Blood Disorders at Children's Medical Center. Access to local

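### The clinical analysis labelled intent-to-treat is a complete-case analysis, with no method for missed visits and no statement of which analysis uses withdrawn subjects' data

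*Combined protocol and SAP*

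**What the plan says.** Section II.c, Statistical Analyses, compares within-patient change in biomarkers, QoL and self-reported activity between arms by t test, "using an intent-to-treat analysis that includes all participants with data at baseline and 6 months". The 6-month value comes from Visit 2: the section on study assessments for both arms refers to the "6 month mark corresponding to Visit 2".

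The Withdrawal/Termination section lists, as its first category, "Subjects that 'No Show' for Visit 2, are unable to provide >80% of the 'steps/day' data and are unable to be contacted/rescheduled". It then adds: "Data already collected will be used in the analysis". It does not say which analysis.

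The sample size paragraph plans 20 per arm, "22 after considering a 20% drop out rate", or 44 in all. The Analyses paragraph counts the trial a success only if loss to follow-up is under 20%. It also promises reasons for dropout and loss by arm, and calls all analyses descriptive. The Primary Aim nevertheless makes effect-size estimates, from change in QoL and biomarkers, part (b) of the primary outcomes.

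Table 1 schedules QoL and biomarkers at Visits 1, 2 and 3, and collects step data in the Fitbit arm only. The only missing-data rule is in Appendix 2, for unanswered PedsQL items. Nothing covers a missed visit, and there is no sensitivity analysis.

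**The concern.** Intent-to-treat means that everyone randomised is analysed in the assigned arm. Requiring a 6-month value makes membership of the set depend on something that happens after randomisation, and whether a subject stays may be related to arm and to outcome. Calling the result intent-to-treat tells readers that this selection is absent.

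Differential loss is plausible. The first withdrawal category refers to step data, which only the Fitbit arm supplies, so it cannot operate alike in both arms. A subject who misses Visit 2 but attends Visit 3 also contributes nothing to the main comparison, although QoL and biomarkers are scheduled at Visit 3.

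At stake are the effect sizes that the pilot is meant to hand on. The sample size paragraph offers them as preliminary data for later studies.

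**Working it through.** **1. Size of the set.** The plan's own dropout step does not reproduce. Twenty evaluable per arm at 20% loss needs 20 / (1 − 0.20) = 25 per arm, not 22. Going from 22 to 20 allows for a loss of only 2/22 = 9.1%. With 22 per arm and 20% loss, 22 × 0.80 = 17.6 per arm remain, about 35 of 44. The largest loss that still meets the success criterion is 8/44 = 18.2% (9/44 = 20.5% fails), which leaves 36.

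**2. Bias formula.** Let f be the share of an arm that is lost, and D the completers' mean change minus the dropouts' mean change, in SD of change. The all-randomised mean is (1 − f) × completers + f × dropouts, so the completers' mean is off by f × D. The bias in the arm difference is f(Fitbit) × D(Fitbit) − f(control) × D(control).

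The documents give no value for D, so the values below are assumptions. Negative values of D reverse the sign.

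| f Fitbit / control | D Fitbit / control | Bias (SD) |
|---|---|---|
| 0.20 / 0.20 | 0.5 / 0.5 | 0.10 − 0.10 = 0 |
| 0.20 / 0.20 | 0.5 / 0 | 0.10 |
| 0.20 / 0.20 | 1.0 / 0 | 0.20 |
| 0.30 / 0.10 | 0.5 / 0.5 | 0.15 − 0.05 = 0.10 |
| 8/22 / 0 | 0.5 (Fitbit) | 0.18 |
| 8/22 / 0 | 1.0 (Fitbit) | 0.36 |

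The last two rows are an extreme: all eight tolerated losses fall in one arm.

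**3. Yardstick.** The standard error of the difference with 18 per arm is √(2/18) = 0.33 SD.

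**4. Simulation of direction and remedy.** Assumptions: 22 per arm, no true effect, higher is better, baseline and follow-up with unit SD and correlation 0.5. The SD of change is then √(2 − 2 × 0.5) = 1. Control loss is 20% at random. Fitbit loss is about 20% and follows a logistic model in either baseline or the change itself; the slope is assumed.

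| Fitbit dropout depends on | Change scores, complete cases | Baseline-adjusted, same cases |
|---|---|---|
| low baseline | about −0.09 SD | 0.00 |
| high baseline | about +0.09 SD | 0.00 |
| poor change | about +0.18 SD | about +0.13 SD |

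The sign in the first two rows comes from regression to the mean: subjects who start low tend to rise, so losing them lowers the arm's mean change. Baseline adjustment also reduced the SD of the estimate from about 0.34 to 0.30.

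**5. The withdrawal sentence beside the analysis set.** A subject withdrawn under the first category has no Visit 2 value and so has no change from baseline to 6 months. Such data can still serve the consent, adherence and retention figures and the baseline description. Both statements can be followed if the withdrawal sentence means those analyses. They conflict only if it means the clinical comparison.

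**The case against.** The defence is that this is a 44-subject pilot with descriptive analyses and a stated caution about its size. The set is defined in the same sentence as its label, and loss by arm with reasons will be reported. Visit 2 has a ±4-week window and rescheduling is attempted, so few subjects will miss Visit 2 and then attend Visit 3. The assumed bias is also smaller than the standard error. All of this stands, and it limits the weight of the point. It does not make the label right, and describing dropout does not correct an estimate.

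A reader might infer that the plan contradicts itself over withdrawn subjects. The text does not support that, because it does not say which analysis will use their data (step 5).

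A reader might also infer that leaving out dropouts flatters the Fitbit arm. Nothing in the documents fixes the direction. If subjects with a poor baseline leave, the bias goes against the Fitbit arm; it favours that arm if those with a good baseline leave or if poor responders leave.

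The defence is also right that, when loss depends on baseline, the fault lies in the unadjusted change score: adjusting within the same complete cases removes the bias.

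**Conclusion.** The point holds in a limited form. The clinical set is complete case and should not be called intent-to-treat. With planned dropout and no method for missed visits, the arm difference may be biased either way, by about 0.1 to 0.2 SD under the central assumptions. It is more if losses fall in one arm, and zero if loss rates and the gap between completers and dropouts are the same in both arms. These sizes rest on assumed gaps, because the documents give none. The statement on withdrawn subjects' data is an ambiguity to be resolved.

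This does not undermine the feasibility outcomes. It should be corrected because effect-size estimation is a stated primary outcome and the correction is cheap.

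**What to change.** - In Statistical Analyses, call the present set complete case, analysed by assigned arm.
- In Withdrawal/Termination, state which analyses use data from withdrawn subjects.
- For measures with a Visit 1 value, replace the unadjusted t test on change with a baseline-conditioned comparison at Visit 2. One option is a mixed model using all available Visit 2 and 3 data for measures collected at those visits. Enter the Visit 1 value as a covariate or as an outcome, not both. As a covariate, subjects with only a baseline value contribute nothing; as an outcome, they remain in the model.
- Define baseline as Visit 1 for this purpose. Statistical Analyses now defines it as levels at diagnosis or before the VTE, whereas Table 1 takes the first study samples at Visit 1.
- State a separate set for PTS. Its change from 6 to 9 months needs Visits 2 and 3, and Table 1 has no PTS assessment at Visit 1.
- Report missingness by arm and visit, and keep the present complete-case change-score analysis as a sensitivity analysis.

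The cost is revised wording and slightly more analysis, with no new data. The model assumes that data are missing at random, and it does not remove bias if dropout depends on unobserved response. In the simulation it was a partial remedy in that case (about 0.18 to 0.13 SD).

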to a post-DVT activity regimen in children. I propose a validated, fitness tracker, the Fitbit, to improve adherence to a 16-week activity regimen in a pilot randomized controlled trial (RCT), in which 44 subjects with DVT will be assigned to the intervention group or to a comparison group. The primary outcomes will consist of a) feasibility indicators determined *a priori* (eligibility, consent, adherence, retention) and b) estimates of effect size associated with the prescribed activity regimen, by describing within-subject change in QoL and 'potential' biomarkers of PTS pre and post intervention in each group.

STUDY DESIGN (Figure 2)

The study design is that of a pilot RCT to test the feasibility of the proposed activity tracker to increase activity in children post DVT, against standard practice, which currently consists of providing education about PTS and instructions to 'be active'. I will use a validated activity tracker, the Fitbit and its data platform- the Fitabase.

METHODS

I. STUDY SETTING

All newly diagnosed patients with first, lower extremity DVT diagnosed at Children's Health System of Texas (CHST) or referred to the Hemostasis Thrombosis Center (HTC) at CHST who have completed 12 weeks (± 2 weeks) of anticoagulation therapy, will be approached for recruitment.

II. ELIGIBILITY CRITERIA

Parents must provide written, informed consent before any study procedures occur.

INCLUSION CRITERIA	RATIONALE
1. Age 7-21 years	VTE is seen across all age groups
2. A radiologically confirmed, acute, proximal (iliofemoral and femoropopliteal) first lower extremity DVT and/or confirmed,	Population with proximal DVT and/or PE deemed to be at highest risk of PTS

acute pulmonary embolism (unilateral or bilateral)	
3. 12 weeks (± 2 weeks) after starting anticoagulation	To mitigate the small theoretical risk of clot dislodgement with activity soon after DVT diagnosis
4. Out-patient ambulatory status	Protocol involves increasing activity

EXCLUSION CRITERIA	
1. Contraindication to increasing activity such as patients with juvenile arthritis, poor balance, congestive heart failure etc.	Protocol involves increasing activity

III. STUDY PROTOCOL

The study has 3-4 planned visits, which will coincide with the standard of care visits.

Screening

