- 1. **Intervention (Fitbit) arm.** The intervention arm will wear a Fitbit for a 16-week period (**Figure 2**). **General Principles of an aerobic activity regimen:**

As the principal muscles affected by PTS are the lower limb muscles, we have opted to use a walking-jogging program to capture steps/day by the Fitbit. This will target all potentially affected muscles (quadriceps, hamstrings and gastrocnemius/soleus). If preferred by the subject, other weight bearing exercises could replace the walk/jog, for example, dancing or team sports such as basketball or volleyball. Because of the unfamiliarity with activity trackers, subjects will be provided with hands-on training to promote successful use of the Fitbit and Fitabase.

a. Schedule and procedures (Table 1): After consent (baseline visit), subjects in this arm will receive a standardized 15-20 minute education session on PTS (what constitutes PTS, why patients get it, how to manage it) and enhanced activity after DVT. Subjects will be asked to wear the Fitbit for a period of four weeks to establish baseline or 'habitual' activity. Using steps/day data received at the end of four weeks, we will determine an individualized activity prescription of 'target steps/day', corresponding to a 25% increase above the baseline.

Table 1	Visit 1	Visit 2	Visit 3
	12 wks post DVT Dx (\pm 2 weeks)	16 wks after Visit 1 (\pm 4 weeks)	8 wks after Visit 2 (\pm 4 weeks)
	SOC Visit	SOC Visit	SOC Visit (Exit Visit)
ALL SUBJECTS			
Informed Consent	X*		
Full Medical History and Exam	X	X	
Biomarker Testing [^]	X\$	X	X
FXIII, D-dimer, CRP	X	X	X ^{^^}
QOL forms	X	X	X
PTS Assessment		X	X
ECS and Log	X	X~	X~
Activity Logs/ Questionnaire	X	X	X
Medication Log***	X	X	X

Phone Calls (monthly)	X	X	
Formal Education Session	X		
Honoraria**	X	X	X
SUBJECTS IN FITBIT ARM			
Hands on Fitbit Training	X		
Steps/Day Data (weekly)	X	X	X
Phone Calls (weekly)	X	X	
Return Fitbit			X

*Informed consent can occur any time after DVT diagnosis until Visit 1; ^Biomarker testing includes: D-Dimer, FVIII, Thrombin generation, markers of fibrinolysis; \$Biomarker testing at Visit 1 may be combined with other SOC labs for those still on anticoagulation at this time; ~ only ECS logs; ** \$25 at Visit 1 and 2, and \$50 at Visit 3; ***Medication logs only for participants on Rivaroxaban or Xarelto; ^^Factor VIII, D-dimer, and CRP can be completed as research procedures at Visit 3 for participant's whose values were within normal range at Visit 2.

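### The change analysis takes baseline at diagnosis or before the clot, but at least five of its nine measures are first collected at Visit 1, about 12 weeks after diagnosis

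*Combined protocol and SAP*

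**What the plan says.** Section II.c, Statistical Analyses, describes the clinical endpoints as "within-patient change from baseline (diagnosis or pre-VTE levels) to 6 months (mean, SD". The population is set by "using an intent-to-treat analysis that includes all participants with data at baseline and 6 months", so a participant needs a value at that baseline to be counted. The group changes are then compared by t test.

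Other sections point to a different starting point:

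- The Primary Aim describes "within-subject change in QoL and 'potential' biomarkers of PTS pre and post intervention in each group".
- Section VII, Outcomes and Power Calculations, makes change in clinical outcomes a primary outcome, "such as PTS biomarkers at baseline and Visit 2, and QoL (at all visits".
- The Analyses paragraph of the same section describes change "from baseline to 6 month, in the QoL scores and PTS biomarkers", with no mention of diagnosis.
- Section III.b has "After consent (baseline visit), subjects in this arm will receive a standardized 15-20 minute education session on PTS". Table 1 places that education session at Visit 1, 12 ± 2 weeks after diagnosis.

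**The concern.** The stated baseline lies before the point at which the study begins to collect data. For a measure with no value at diagnosis or before the clot, neither the change score nor the analysis set can be formed as written. The phrase also joins two different time points with an 'or' and does not say which applies to which measure.

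Two things are at stake. First, change in biomarkers and QoL is a listed primary outcome, and the pilot's purpose is to estimate effect size from within-subject change in each arm. A change that starts at diagnosis includes recovery that took place before any intervention. Second, where two candidate baselines exist, as for self-reported activity, the analyst could choose between them after seeing the data.

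**Working it through.** No figure in the plan depends on the baseline definition. Its one power figure, 71% for PTS falling from 26% to 10%, does not use a change from baseline. It reproduces as 70.9% with 22 per arm, a one-sided pooled test and p<0.2, and this point does not alter it.

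**Step 1: the measures.** Section II.c lists nine measures with a baseline-to-6-month change, counting thrombin and QoL sub-measures separately. PTS is left out because the section gives it its own 6-to-9-month window.

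**Step 2: where a diagnosis or pre-clot value could come from.** The possible sources are Table 1, the laboratory item under Baseline Assessments (III.a), the biomarker and QoL items under Study assessments for both arms, and the Appendix 5 forms. The blood volume is a cross-check: 4.5 teaspoons in total at 1.5 per visit gives 4.5 / 1.5 = 3 research draws, which matches Visits 1, 2 and 3 and leaves none at diagnosis.

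| Measure | Diagnosis or pre-clot value? | Visit 1 and Visit 2 values? |
|---|---|---|
| Endogenous thrombin potential | No | Yes |
| Peak thrombin | No | Yes |
| Fibrinolysis on thromboelastography | No | Yes |
| QoL total | No | Yes |
| QoL physical | No | Yes |
| D-dimer | Only if drawn in routine care | Yes |
| FVIII | Only if drawn in routine care | Yes |
| CRP | Only if drawn in routine care | Yes |
| Self-reported activity | Yes, by recall | Yes |

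On the three routine labs, the Table 1 footnote says "Factor VIII, D-dimer, and CRP can be completed as research procedures at Visit 3" under a stated condition, which suggests that they are normally routine tests. (The table row prints FXIII; the footnote and text say FVIII.) No diagnosis draw is scheduled, however, and the III.a laboratory item names none of the three. Patients referred in or first treated elsewhere are eligible, so their diagnosis labs may be uneven.

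**Step 3: counts.**

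- No value even if all three routine labs were drawn: 5 of 9.
- No value on the visit schedule alone: 5 + 3 = 8 of 9.
- With thrombin generation and QoL each counted once: 3 of 7 and 6 of 7.
- No value with Visit 1 as baseline: 0 of 9.

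**Step 4: timing for the three routine labs.** Visit 1 is 12 ± 2 weeks after diagnosis and Visit 2 is 16 ± 4 weeks after Visit 1, so Visit 2 falls nominally at 12 + 16 = 28 weeks. The share of a diagnosis-based interval that precedes Visit 1 is V1 / (V1 + gap):

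- nominal: 12 / (12 + 16) = 0.43
- lowest: 10 / (10 + 20) = 0.33
- highest: 14 / (14 + 12) = 0.54

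The 8-week target-step period is 8 / 28 = 29% of a diagnosis-based interval and 8 / 16 = 50% of a Visit 1-based one.

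**Step 5: effect on the comparisons.** Both candidate baselines precede the intervention, so randomisation protects the between-arm contrast from systematic bias. Precision may be lower if a diagnosis value is less closely related to the 6-month value than a Visit 1 value is. The documents give no SD or correlation, so no figure is offered. The within-arm change has no such protection.

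**The case against.** The strongest reply is that the rest of the protocol already resolves the matter. The aim, the outcomes section and the schedule all point to study entry, and for the five research-only measures Visit 1 is the only pre-intervention value. A sensible analyst would use it. The analyses are also declared descriptive ("All analyses will therefore be descriptive and will be performed once, at the end of the trial"), the success criteria do not use these change scores, and the between-arm contrast is not biased. On that view this is a wording clean-up.

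Much of that is fair, and it limits the seriousness of the point. It does not remove it. The other sections show what the baseline should be, but the section that governs the calculation states something else. Calling the analyses descriptive does not help either, because these descriptive estimates are what the pilot is meant to deliver.

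Four narrower objections deserve an answer:

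- **Eight of nine is a schedule-only count.** This is correct: a schedule that starts at 12 weeks cannot contain a diagnosis value. Five of nine is the firm figure.
- **Consent may come earlier than Visit 1, possibly in hospital.** This is also correct, so placing the baseline visit at Visit 1 is an inference. It is a strong one, because the session given at that visit is at Visit 1 in Table 1 and no research assessment is scheduled before it.
- **Share of time is not share of biomarker change.** This is accepted. The percentages describe the interval only.
- **Return towards pre-clot activity is a legitimate contrast.** It is, and it can be kept under its own label. It does not measure change over the intervention.

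**Conclusion.** The concern holds: the baseline rule is wrong as written. It cannot be applied to five of nine measures on the reading most favourable to the plan, or to eight of nine if only scheduled collections count. For D-dimer, FVIII and CRP it would make the analysis set depend on what was drawn before enrolment and, nominally, place 43% of the interval before study entry (33% to 54%).

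The consequence is confined to the biomarker, QoL and activity change scores. The PTS analysis and the feasibility criteria do not change. The counts assume that routine records hold no thrombin generation, thromboelastography or QoL values from diagnosis; nothing in the plan suggests that they do. A Visit 1 baseline reduces, but does not eliminate, natural recovery within each arm. The wording should be corrected before analysis so that the baseline is not chosen with results in view.

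**What to change.** In section II.c, delete the parenthetical that sets baseline at diagnosis or before the clot. Replace it with a statement that baseline is the Visit 1 value, taken before randomised treatment starts, for all biomarkers, both QoL scores and current self-reported activity.

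For activity, name the score. The initial form in Appendix 5 already has a field for the Godin score after diagnosis as well as one for before it. The PAQ line that follows the after-diagnosis Godin field is labelled as a before-diagnosis score for a second time; correct that label if PAQ is to be analysed.

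Diagnosis labs, where they exist, and change from recalled pre-clot activity may be reported as separately labelled supplementary comparisons. Leave the 6-to-9-month window for PTS as it is.

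The essential change is one phrase, plus a short sentence naming the activity score and, if needed, a form-label correction. Table 1 already schedules Visit 1 and Visit 2 collection for all nine measures, so no new visits, blood or data are needed.
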